9.2.3 Case Report Forms

An investigator is required to prepare and maintain adequate and accurate case histories designed to record all observations and other data pertinent to the investigation on each individual treated or entered as a control in the investigation. Data reported on the CRF that are derived from source documents must be consistent with the source documents or the discrepancies must be explained.

For sites using the BMS electronic data capture tool, electronic CRFs will be prepared for all data collection fields except for fields specific to SAEs and pregnancy, which will be reported on the paper or electronic SAE form and Pregnancy Surveillance form, respectively. Spaces may be left blank only in those circumstances permitted by study-specific CRF completion guidelines provided by the sponsor.

The confidentiality of records that could identify subjects must be protected, respecting the privacy and confidentiality rules in accordance with the applicable regulatory requirement(s).

The investigator will maintain a signature sheet to document signatures and initials of all persons authorized to make entries and/or corrections on CRFs.

The completed CRF, including any paper or electronic SAE/pregnancy CRFs, must be promptly reviewed, signed, and dated by a qualified physician who is an investigator or subinvestigator. For electronic CRFs, review and approval/signature is completed electronically through the BMS electronic data capture tool. The investigator must retain a copy of the CRFs including records of the changes and corrections.

Each individual electronically signing electronic CRFs must meet BMS training requirements and must only access the BMS electronic data capture tool using the unique user account provided by the sponsor. User accounts are not to be shared or reassigned to other individuals.

9.3 Clinical Study Report and Publications

A Signatory Investigator must be selected to sign the clinical study report.

For this protocol, the Signatory Investigator will be selected considering the following criteria:

- External Principal Investigator designated at protocol development
- National Coordinating Investigator
- Subject recruitment (eg, among the top quartile of enrollers)
- Involvement in trial design
- Other criteria (as determined by the study team)

The data collected during this study are confidential and proprietary to the sponsor. Any publications or abstracts arising from this study require approval by the sponsor prior to publication or presentation and must adhere to the sponsor's publication requirements as set forth in the approved clinical trial agreement (CTA). All draft publications, including abstracts or detailed summaries of any proposed presentations, must be submitted to the sponsor at the earliest practicable time for review, but at any event not less than 30 days before submission or presentation unless otherwise set forth in the CTA. Sponsor shall have the right to delete any confidential or proprietary information contained in any proposed presentation or abstract and may delay publication for up to 60 days for purposes of filing a patent application.

10 GLOSSARY OF TERMS

Term	Definition
Adverse Reaction	An adverse event that is considered by either the investigator or BMS as related to the investigational product
Unexpected Adverse Reaction	An adverse reaction, the nature or severity of which is not consistent with the applicable product information (eg, Investigator Brochure for an unapproved investigational product)
Expected Adverse Event	An event that is described or mentioned in the applicable (current version) or the prescribing information for the drug (eg, Investigator Brochure for an investigational product, approved local label for a marketed product).
Serious Adverse Event	
Serious adverse event defined as any untoward medical occurrence that at any dose: results in death; is life threatening (defined as an event in which the subject was at risk of death at the time of the event; it does not refer to an event which hypothetically might have caused death if it were more severe), requires inpatient hospitalization or causes prolongation of existing hospitalization; results in persistent or significant disability/incapacity, is a congenital anomaly/birth defect; is an important medical event (defined as a medical event(s) that may not be immediately life threatening or result in death or hospitalization but, based upon appropriate medical and scientific judgment, may jeopardize the subject or may require intervention [eg, medical, surgical] to prevent one of the other serious outcomes listed in the definition above). Examples of such events include, but are not limited to, intensive treatment in an emergency room or at home for allergic bronchospasm; blood dyscrasias or convulsions that do not result in hospitalization.). For reporting purposes only, BMS also considers the occurrence of pregnancy, overdose (regardless of association with an AE), and cancer as important medical events.

Investigational Product	An investigational product, also known as investigational medicinal product in some regions, is: A pharmaceutical form of an active substance* being tested or used as a reference in a clinical study, including products already with a marketed

Term	Definition
	authorization but used or assembled (formulated or packaged) in a way different from the authorized form, or used for an unauthorized indication, or when used to gain further information about the authorized form. * The only investigational product is apixaban.
Noninvestigational Product	Support, escape (rescue) or diagnostic medications (marketed form), concomitant medications.

11 LIST OF ABBREVIATIONS

Term	Definition
ACC	American College of Cardiology
AE	adverse event
ALT	alanine aminotransferase
ANC	Absolute neutrophil count
aPTT	activated partial thromboplastin time
AST	aspartate aminotransferase
BA/BE	bioavailability/bioequivalence
BID	twice daily
BMI	Body Mass Index
BMS	Bristol-Myers Squibb
BUN	blood urea nitrogen
CBC	complete blood count
CHF	Congestive heart failure
CK	creatine kinase
CK-MB	Creatine kinase MB subunit
CFR	Code of Federal Regulations of the United States of America
CRNM	clinically relevant non-major bleeding
CRP	C-reactive protein
CT	Computer tomography
CUS	compression ultrasound
DBP	Diastolic blood pressure
DSMB	Data Safety Monitoring Board
DVT	deep-vein thrombosis
ECG	electrocardiogram
e-CRF	electronic case report form
ERC	Ethics Review Committee
ESR	Expedited safety report
FSH	follicle-stimulating hormone
GGT	gamma-glutamyl transpeptidase

Term	Definition
HAV	hepatitis A virus
Hb	hemoglobin
HbsAg	hepatitis B surface antigen
HBC	hepatitis B core antigen
HCG	human chorionic gonadotropin
HCV	hepatitis C virus
HIV	Human Immunodeficiency Virus
HRT	hormone replacement therapy
ICAC	Independent Central Adjudication Committee
IEC	International Ethics Committee
INR	International normalized ratio
IRB	Institutional Review Board
ITT	intent-to-treat
IVRS	Interactive Voice Response System
kg	kilogram
LFT	liver function test
LMWH	low molecular weight heparin
MedDRA	Medical Dictionary for Regulatory Activities
MCV	Mean Corpuseular Volume
MH	Mantel-Haenszel
MCH	Mean Corpuseular Hemoglobin
MCHC	Mean Corpuseular Hemoglobin Concentration
MI	myocardial infarction
MRI	Magnetic Resonance Imaging
NSAIDs	Non-Steroidal Anti-Inflammatory Drugs
PCI	percutaneous coronary intervention
PE	pulmonary embolism
PO	Per os (Latin by mouth)
PT	Prothrombin time
RBC	Red blood cell

Term	Definition
QD	once daily
SAE	serious adverse event
SBP	Systolic blood pressure
SGOT	Serum Glutamic Oxaloacetic Transaminase
SGPT	Serum Glutamic Pyruvic Transaminase
THR	Total hip replacement
TKR	total knee replacement
ULN	Upper limit of normal
US	Ultrasound
VKA	Vitamin K antagonist
VTE	Venous thromboembolism
V/Q	Ventilation perfusion scan
WBC	White blood cell
WOCBP	women of childbearing potential

[REDACTED]

[REDACTED]

[REDACTED]

[REDACTED]

[REDACTED]

[REDACTED]

**PROTOCOL CV185158**

**V2.0**

## DOCUMENT HISTORY

Version Number	Author(s)	Description
1.0		Original Version
2.0		1.Efficacy is not primary endpoint. There is no sensitivity analysis on evaluable population needed. Thus the definition of evaluable population and corresponding planned analyses were deleted now. 2. Original treatment compliance formula is not accurate. It's adjusted to current version.

### 1.1 Research Hypothesis

Apixaban 2.5 mg twice a day in Indian patients undergoing hip or knee replacement surgery will provide an acceptable rate of ISTH major/CRNM bleeding.

### 1.2 Schedule of Analyses

A final analysis will be performed after all subjects either complete the 2 weeks (for knee replacement subjects) or 5 weeks (for hip replacement subjects) treatment period followed by a 30-day follow-up period, or discontinue prematurely. There is no interim analysis planned for this study.

## 2 STUDY DESCRIPTION

[figure not shown]
### 2.1 Study Design

Expected duration of the study, from first subject, first visit through last subject, last visit is approximately 8 months.

This study is designed to evaluate the safety of oral apixaban 2.5 mg BID following total knee and hip replacement surgeries. There are four study periods extending up to maximum duration of approximately  $42 \pm 2$  days for the patients undergoing total knee replacement surgery and up to  $65 \pm 2$  days for the patients undergoing total hip replacement surgery:

- A screening period, of up to 14 days prior to surgery
- An enrollment period: from 4 days before surgery to 1 day after surgery
- A treatment period: First dose, PO, starting 12 - 24 hours after completing skin wound closure, then BID for  $35 \pm 2$  days for the subjects undergoing total hip replacement or  $12 \pm 2$  days for the subjects undergoing total knee replacement.
- A 30-day follow-up period starting the day after the last dose of study medication.

**Figure 2.1 Study Design**

## **2.2 Treatment Group Assignment**

Apixaban 2.5 mg bid.

## **2.3 Blinding and Unblinding**

Not applicable.

## **3 OBJECTIVES**

### **3.1 Primary Objective**

To evaluate that oral administration of apixaban 2.5 mg twice a day for 2 weeks (for knee replacement subjects) or 5 weeks (for hip replacement subjects) is well tolerated in Indian subjects and produces an acceptable rate of ISTH major/CRNM bleeding.

### **3.2 Secondary Objectives**

To evaluate that oral administration of apixaban 2.5 mg twice a day for 2 weeks (for knee replacement subjects) or 5 weeks (for hip replacement subjects) produces an acceptable rate of the composite of VTE/all cause death.

## **4 ENDPOINTS**

### **4.1 Primary Endpoint**

The primary study endpoint is a composite of International Society on Thrombosis and Haemostasis (ISTH) major bleeding/clinically relevant non-major bleeding (CRNM) in subjects undergoing elective total knee or hip replacement at the end of treatment + 2 days, where ISTH major bleeding is

- Fatal or
- Bleeding in a critical organ, such as brain, spine, eye, retroperitoneum, joint, heart sac, or skeletal muscle (and resulting in compartment syndrome), or

- Bleeding that results in a fall of hemoglobin of 2 g/dL or more or transfusion of 2 units or more of packed red cells or whole blood within 24 hours

and CRNM bleeding is bleeding that

- Is clinically acute and overt
- Does not satisfy criteria as a major bleed but requires medical intervention, such as a visit to a physician's office, emergency room, or urgent care center for epistaxis.

## 4.2 Secondary Endpoint

The secondary endpoint will be: The composite of VTE/all cause death at the end of treatment + 2 days, where VTE is the combination of deep vein thrombosis and non-fatal pulmonary embolism.

## 5 SAMPLE SIZE AND POWER

The sample size of the study is determined by requirement of regulatory agency rather than statistical considerations. With 500 subjects in the apixaban arm and event rate of 4.36% for ISTH major or clinically relevant non-major bleeding, the width of the 95% CI for the event rate will be (2.6%, 6.2%) and width of the CI is 3.6%.

## 6 STUDY PERIODS, TREATMENT REGIMENS AND POPULATIONS FOR ANALYSES

### 6.1 Study Periods

In all listings, summaries and statistical analyses, the term '**Intended Treatment Period**' refers to the period that starts with the enrollment.

In all listings, summaries and statistical analyses, the term '**Treatment Period**' will refer to the period between the first administration of study medication (post-surgery oral apixaban) and 2 days after the last administration of study medication (end of treatment). This period will be the basis for the summaries of safety and efficacy.

In all listings, summaries and statistical analyses, the term "**Follow-up Period**" will refer to the period starting after the "Treatment Period" ended through 30 days after discontinuation of study drug (for treated subjects).

### 6.2 Treatment Regimens

Safety and efficacy outcomes will be summarized according to the **Treated** group, which subjects who received at least one dose of study drug.

### 6.3 Populations for Analyses

The following populations will be used for the analyses:

### **Enrolled Population**

The Enrolled Subjects population consists of all subjects who signed informed consent.

### **Treated Population**

The treated population consists of all subjects who received at least one dose of study drug during the treatment period. In the treated population, subjects are categorized to the **As Treated** group.

### **Efficacy Population**

Same as Treated Population.

## **7 STATISTICAL ANALYSES**

Type of surgery (knee surgery or hip surgery) will be included as subgroup factor in some of the efficacy ([Section 7.5](#)) and all safety summaries ([Section 7.6](#)) as well as when summarizing demographic and baseline characteristics ([Section 7.3](#)) and extent of exposure ([Section 7.4](#)).

### **7.1 General Methods**

Refer to Section 7.1 of the Core SAP for VTE Prevention for further details on statistical methods.

### **7.2 Study Conduct**

Significant protocol deviations will be identified for all subjects who are treated.

### **7.3 Study Population**

#### **7.3.1 Subject Disposition**

Refer to Section 7.3.1 of the Core SAP for VTE Prevention.

#### **7.3.2 Demography and Baseline Characteristics**

Demographic and baseline characteristics will be summarized for all subjects combined, using treatment data set. All summaries will be further tabulated by stratification factor of type of surgery (knee or hip). Continuous variables will be summarized using mean and standard deviation. Categorical variables will be summarized using relative frequency.

Key demographic and baseline variables to be summarized include: age, gender, race, vital signs (systolic blood pressure, diastolic blood, pressure, and heart rate), medical history, knee or hip replacement surgery experience, intra-operative details, and post-surgical patient care characteristics.

## 7.4 Extent of Exposure

### 7.4.1 Study Therapy

Extent of exposure to the study drug is defined as the number of the days the subject is known on study drug. Summary to exposure to study drug will show the distribution of the number of days on drug, together with the mean days of exposure, by type of surgery (knee or hip).

Treatment compliance (TC) will also be summarized by type of surgery (knee or hip).

For each treated subject, treatment compliance with apixaban (BID) regimen is defined as follows:  $TC = \frac{100 * \text{number of tablets taken}}{\text{number of days from first to last post-surgery open label dose} * 2 - k} \%$

where

- k=0, if the first dose is given the day after surgery
- k=1, if the first dose is given on the day of surgery.

In addition, time from the end of surgery to first post-operative dose of study medication will be summarized by type of surgery (knee or hip).

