3.1.3 Treatment Period

The day of surgery is Day 1.

The first dose of apixaban will be administered 12 - 24 hours after completing skin wound closure, typically in the morning of Day 2 and then BID for 35 ± 2 days for the subjects undergoing total hip replacement or 12 ± 2 days for the subjects undergoing total knee replacement.

While hospitalized, subjects will be evaluated on Day 1, Day 2 and discharge day for suspected symptomatic VTE, bleeding events or any AEs or SAEs.

At any subsequent treatment visits (Day 7 ± 2 and Day 12 ± 2 for TKR subjects or Day 7 ± 2 and Day 35 ± 2 for THR subjects), subjects will be instructed to report to the investigator all AEs, including signs and/or symptoms suggestive of VTE and any bleeding events they experienced since their last visit. Subjects with signs and/or symptoms of VTE at any time should return to the hospital/clinic and undergo appropriate diagnostic evaluation.

If study medication is discontinued for a suspected DVT and or PE, alternative antithrombotic prophylaxis may be initiated per the Investigator's discretion and standard of care. Every effort

must be made to confirm a suspected DVT and/or PE diagnosis before discontinuing study medication and initiating treatment per the Investigator's standard of care.

Samples for laboratory assessment of hematology will be obtained on the day of discharge.

Urine pregnancy test will be performed on Day 12 for TKR subjects and on Day 35 for THR subjects.

Dosing Diaries should be collected at Day 7 & Day 12 for TKR subjects and at Day 7 & Day 35 for THR subjects.

Subjects should be encouraged to return for an in person visit on Day 7 and Day 12 for TKR and Day 7 and Day 35 for THR. Alternatively those visits would be performed by phone.

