4.3 Selection and Timing of Dose for Each Subject

Study medication for this study is defined as apixaban 2.5 mg tablets. Subjects will receive apixaban tablets.

- The first oral dose will be given 12 - 24 hours after completing skin wound closure, typically in the morning of Day 2, followed by BID dosing for 12 ± 2 days in subjects undergoing TKR or 35 ± 2 days in subjects undergoing THR.
- Study subjects will take one tablet in the morning and one tablet in the evening.

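### SAP 7.4.1 miscounts the tablets due in the compliance ratio, so some subjects who miss no dose score below 100%

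*SAP*

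**What the plan says.** SAP 7.4.1 (Study Therapy) defines treatment compliance, TC, as a percentage. The numerator is the "number of tablets taken". The denominator is the "number of days from first to last post-surgery open label dose", times 2, minus k. Two values of k are given: "k=0, if the first dose is given the day after surgery" and "k=1, if the first dose is given on the day of surgery". TC is to be summarised by knee or hip surgery. The same section summarises days on drug and the time from end of surgery to the first dose, both by surgery type.

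On timing, Protocol 3.1.3 states "The day of surgery is Day 1", so the day after surgery is Day 2. Protocol 4.3 states "The first oral dose will be given 12 - 24 hours after completing skin wound closure, typically in the morning of Day 2". It then sets twice-daily dosing for 12 ± 2 days (knee) or 35 ± 2 days (hip), and adds: "Study subjects will take one tablet in the morning and one tablet in the evening".

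The SAP document history says of version 2.0: "Original treatment compliance formula is not accurate. It's adjusted to current version". It does not say what the earlier inaccuracy was.

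**The concern.** The correction k has a clear purpose. It removes one tablet from the expected count when only one dose fits on the first day. The SAP applies it only to starts on the day of surgery and treats every Day 2 start as a full two-tablet day, whatever the hour. The last dosing day has no matching correction. Both gaps charge a subject with a tablet that was never due, and TC then reports a missed dose that did not occur.

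What is at stake is the accuracy of one descriptive table. One miscounted tablet weighs more on a short course than on a long one. The error is therefore larger for knee than for hip, and the planned summary by surgery type could show a difference in adherence that comes partly from the formula.

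**Working it through.** **Inputs.** Formula and k: SAP 7.4.1. Two tablets a day, planned durations and first-dose window: Protocol 4.3. Day numbering: Protocol 3.1.3. The documents state no compliance value to reproduce, so the first check is whether the formula works in the cases k was built for.

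**Day count.** The SAP does not say whether both end days are counted. Let D be the number of calendar days on which dosing occurs.
- Inclusive count: a Day 2 morning start with an evening finish gives 2D/(2D) = 100%. A Day 1 evening start with k = 1 gives (2D − 1)/(2D − 1) = 100%.
- Last date minus first date: the same perfect Day 2 morning starter scores 24/22 = 109.1% (D = 12) or 70/68 = 102.9% (D = 35).

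Only the inclusive count makes k work, so it is used below.

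**Is a Day 2 evening start allowed?** The window closes 24 hours after wound closure. A first dose at 18:00 on Day 2 therefore needs closure at 18:00 or later on Day 1. Closure at 14:00 gives a window of 02:00 to 14:00 on Day 2, which excludes the evening. An evening start is thus permitted, but only after a late operation.

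**TC when no dose is missed**, with TC = 100 × tablets/(2D − k):

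| First dose to last dose | Tablets | k | Knee, D = 12 | Hip, D = 35 |
|---|---|---|---|---|
| Day 2 morning to an evening | 2D | 0 | 24/24 = 100% | 70/70 = 100% |
| Day 1 evening to an evening | 2D − 1 | 1 | 23/23 = 100% | 69/69 = 100% |
| Day 2 evening to an evening | 2D − 1 | 0 | 23/24 = 95.8% | 69/70 = 98.6% |
| Day 2 morning to a morning | 2D − 1 | 0 | 23/24 = 95.8% | 69/70 = 98.6% |
| Day 2 evening to a morning | 2D − 2 | 0 | 22/24 = 91.7% | 68/70 = 97.1% |
| Day 1 evening to a morning | 2D − 2 | 1 | 22/23 = 95.7% | 68/69 = 98.6% |

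**Range over the allowed durations.** With k = 0 and one miscounted tablet, TC runs from 19/20 = 95.0% to 27/28 = 96.4% for knee (10 to 14 days), and from 65/66 = 98.5% to 73/74 = 98.6% for hip (33 to 37 days).

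**Short courses.** The shortfall grows as the course shortens. A Day 2 evening starter who takes every tablet and stops on the third dosing day, after the evening tablet, scores 5/6 = 83.3%. A subject who takes one Day 2 morning tablet and is then stopped scores 1/2 = 50%, with nothing missed.

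**Group means.** One miscounted tablet costs 1/24 = 4.2 points for knee and 1/70 = 1.4 points for hip. The fall in a group mean is that figure times the share of subjects affected. The documents do not give the share, so the fall lies between 0 and 4.2 points (knee) or 0 and 1.4 points (hip). With a miscount at both ends, the upper limits are 2/24 = 8.3 and 2/70 = 2.9 points.

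**The case against.** The strongest reply is that little depends on this. The protocol describes a Day 2 morning start as typical, the loss is one or two tablets, and only affected subjects lose anything. No population uses TC: the Treated Population needs one dose, the Efficacy Population is the same, and the evaluable population was deleted in SAP version 2.0. No endpoint or confidence interval uses it either. All of this stands and limits the weight of the point. It does not make the count right, and the morning-finish error also reaches subjects who start at the typical time.

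A second reply is that the correction needs the time of day of both doses. The first-dose time is already needed for the surgery-to-first-dose summary in SAP 7.4.1. For the last dose, Protocol 5.2 says only that the diaries record medication taken, so a morning or evening field is an assumption.

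A reader might go further and infer that the formula is wrong because early stopping goes unpenalised: a hip subject who starts on a Day 2 morning and stops after 3 full days scores 6/6 = 100%, having taken 6/70 = 8.6% of a 35-day supply. The documents do not support calling that 100% an error. A denominator running from first to last dose is a legitimate measure of adherence while on drug, and Protocol 3.4.2 requires discontinuation in several situations that should not be scored as non-compliance. Early stopping is shown elsewhere, in the days-on-drug summary of SAP 7.4.1 and the Kaplan-Meier estimate of early discontinuation in Protocol 8.4.3, although SAP 7.6 does not repeat that estimate. Dividing by planned tablets would bring its own distortion: perfect compliers within the allowed knee durations would score from 20/24 = 83.3% to 28/24 = 116.7%. What remains is a matter of labelling, since the SAP does not say that TC is confined to time on drug.

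**Conclusion.** The point holds as a minor error in a stated rule. SAP 7.4.1 charges tablets that were not due when the first dose falls in the evening of Day 2 or the last dose is a morning one. In a full-length course with no missed dose, the understatement is 4.2 points (12-day knee) or 1.4 points (35-day hip) for one such tablet under k = 0, and 8.3 or 2.9 points for two. It is larger in short courses.

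This rests on inclusive day counting, which the SAP does not state but which k requires, and on one morning and one evening tablet a day. How many subjects are affected is unknown. The primary and secondary results are untouched. That version 2.0 already revised this formula shows only that its accuracy was thought worth correcting; it says nothing about what the earlier fault was.

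**What to change.** In SAP 7.4.1, replace the denominator by expected tablets = 2 × (inclusive calendar days from first to last dose), minus 1 if the first dose was an evening dose, minus 1 if the last dose was a morning dose. Every row of the table above then gives 100%, and so do the two short-course examples. State that both end days are counted. Label the result as on-drug adherence, to be read beside the days-on-drug summary already planned.

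The cost is a few lines of SAP text and programming, plus a check that the time of day of the last dose is recorded. If it is not, the first-dose correction can still be made, and the SAP should state that the last day may be over-counted by one tablet. One limitation comes with the change: a final evening tablet that was due but missed no longer counts against the subject. That is consistent with a measure that ends at the last dose taken, and the label should make it plain.
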